### 5.1.1. Analysis Window

The study date and corresponding study visit/week will be captured on each case report form (CRF). Visit windows will be created around the study day of each scheduled visit. It will be used to aggregate data, which are to be summarized by visit. The visit windows and the targeted study day are indicated in Table 1. Details will be added later if more than one assessment falls within the same visit window. If an assessment is not scheduled for every visit, windows will be combined so that the interval between targeted study days is split evenly and consistently between visits.

**Table 1. Visit Windows**

Scheduled Study Day	Visit Window
Screening	-999, -1
Week 0 Day 1*	1, 7
Week 2 Day 1 (Day 15)	8, 21
Week 4 Day 1 (Day 29)	22, 42
Week 8 (Day 57)	43, 70
Week 12 (Day 85)	71, 98
Safety Follow-up (Week 16)	99, 999
* Study Day 1 begins on the day of randomization. Each Week consists of 7 days.	

## 5.2. Participant Dispositions

The number of participants in the following disposition categories will be summarized throughout the study by intervention group and overall:

- Participants who received study intervention
- Participants who completed the study
- Participants who discontinued study intervention
- Reasons for discontinuation of study intervention
- Participants who terminated study prematurely
- Reasons for termination of study

The distribution of the time to [study termination/discontinuation of study intervention] will be displayed with Kaplan-Meier curves. Participants who terminate study participation

prematurely/discontinue study intervention at any time will be considered an ‘Event’ and their date of study termination/study intervention discontinuation will be used in the time to event calculation. Participants who complete [the study/study intervention] will be censored and the date of [study completion/last dose of study intervention] will serve as the time of censoring.

A listing of participants will be provided for the following categories:

- Participants who discontinued study intervention
- Participants who terminated study prematurely
- Participants who were unblinded during the study period
- Participants who were randomized yet did not receive study intervention.

### 5.3. Primary Endpoint Analysis

**Level of Significance:** In general, all tests will be performed at a 2-sided significance level of 0.1, unless otherwise specified. All interval estimations will be reported using 2-sided 90% confidence intervals (CIs).

Multiplicity adjustment consideration will be based on an overall type I error rate of 0.1 (2-sided). The hypothesis testing will be conducted in a hierarchical manner with the test on the primary endpoint conducted first and the tests on major secondary endpoints conducted next. Within the major secondary endpoints, the sequential gatekeeping approach in conjunction with graphical multiplicity control procedures will be applied. As the interim analysis (IA) will not lead to an early completion due to success, multiplicity adjustment is not required. Nominal p-values will be calculated for all treatment comparisons.

The efficacy analysis of the primary will be based on the full analysis set. Regardless of the actual treatments the participants received, efficacy data will be analyzed according to the initial randomization assignment for the treatment phase.

#### 5.3.1. Definition of Endpoint

The primary endpoint will be change from baseline in the CDAI score at Week 12 based on full analysis set. This will apply for both interim analysis and final analysis.

The CDAI is a validated multi-item measure of severity of illness derived as a weighted sum of 8 different Crohn’s disease-related variables. These 8 variables are:

- extra-intestinal manifestations
- abdominal mass
- weight
- hematocrit
- use of antidiarrheal drug(s) and/or opiate
- total number of liquid or very soft stools
- abdominal pain/cramps

- general well-being.

The last 3 variables are scored over 7 days by the participant on a diary card. For the total number of liquid or very soft stools, abdominal pain/cramps, and general well-being, if only 5 days or 6 days of data are available for the calculation, the weights of 7/5 and 7/6, respectively, will be used for the calculation; if the values are recorded for less than 5 days, the component will not be calculated.

At each timepoint, the CDAI score will only be calculated if  $\geq 4$  of the 8 components are available. If the CDAI score cannot be calculated (ie,  $<4$  components available), the CDAI score will be considered missing. When at least 4 of the 8 components are available, any missing components will be imputed by carrying forward the last non-missing component.

The weight component of the CDAI will be based on the standard weight table (Attachment 5).

Subjects who do not return for evaluation or have a missing CDAI score at Week 12 will be considered to have no change at Week 12 from their baseline CDAI score.

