### **5.3.2. Estimand**

#### **5.3.2.1. Primary Estimand (Estimand 1)**

The primary estimand uses a Composite Strategy that considers meeting the treatment failure (TF) criteria as an unfavorable outcome. This strategy aims to achieve an objective treatment effect.

The primary estimand, the main clinical quantity of interest to be estimated in the study, is defined by the following components:

**Treatment:** Oral tablets CCI [REDACTED] for a 12 week period

- Experimental: JNJ-67864238 (PTG-200), CCI [REDACTED]
- Control: Matching Placebo tablets CCI [REDACTED]

**Population:** Participants with moderately to severely active Crohn's disease, The target population consists of men or women 18 to 75 years of age with moderately to severely active Crohn's disease of at least 3 months' duration, defined as a CDAI score  $\geq 220$  but  $\leq 450$  at Week 0, with an SES-CD score  $\geq 3$  by central endoscopy read. Participants with a screening SES-CD score  $< 3$  can be randomized and received at least one study dose if they have an elevated CRP ( $> 0.3$  mg/dL or 3.0 mg/L) or elevated fecal calprotectin ( $> 250$   $\mu\text{g/g}$ ). Participants must have colitis, ileitis, or ileocolitis previously confirmed at any time in the past by radiography, histology, and/or endoscopy. Participants must be biologic intolerant or refractory (Bio-IR) or biologic nonfailures (Bio-NF) and must be on a stable dose of at least 1 protocol-permitted therapy for the treatment of Crohn's disease prior to baseline and not receiving any protocol-prohibited therapies. For more details and for a complete list of inclusion/exclusion criteria, please refer to the protocol.

**Variable (Endpoint):** Change from baseline in the CDAI score at Week 12. Participants who have intercurrent events in categories 1-3 (defined below) prior to the Week 12 visit will have their baseline CDAI score assigned, regardless of the observed data.

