### Intercurrent Events and Corresponding Strategies:

The following are the intercurrent events considered for this trial:

1. A Crohn's disease-related surgery (with the exception of minor procedures such as drainage of a superficial abscess or seton placement, etc.);
2. A prohibited change in CD medication;
3. Discontinuation of study intervention due to lack of efficacy or an AE of worsening Crohn's disease;
4. Discontinuation of study intervention due to COVID-19 related reasons (like missing the assessment visit due to COVID-19 quarantine, but excluding COVID-19 infection)
5. Discontinuation of study intervention due to reasons other than lack of efficacy or an AE of worsening Crohn's disease (including AE/SAE due to COVID-19 infection).

Intercurrent events (ICEs) in categories 1-3 will be handled by the composite strategy, and ICE category 4 will be handled by the hypothetical strategy (as if subjects would have not experienced this intercurrent event), and ICE category 5 will be handled by the treatment policy strategy. The composite strategy assesses the treatment effects not only based on the variable measurements, but also based on intercurrent events. This estimand acknowledges that having an intercurrent event in categories 1-3 is an unfavorable outcome, ie. baseline value will be used after ICEs. For subjects experiencing ICE category 4, CDAI data at all visits after an ICE will be set to missing with

assumption of missing at random. For ICE category 5, treatment policy strategy, the observed values after ICEs will be used, if available.

**Population-level summary:** The difference of change in the CDAI score at Week 12 between the Experimental treatment group and the placebo treatment group.

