### 5.3.3. Analysis Methods

#### 5.3.3.1. Main Estimator (Analysis) for the Primary Estimand

The primary analysis will be based on the full analysis set which will include all participants randomized and who receive at least 1 dose of the study intervention. Participants in the efficacy analyses will be summarized according to their assigned treatment arm regardless of whether or not they receive the assigned study intervention. The primary endpoint will be analyzed based on the primary estimand.

Data used in the primary analysis (i.e. the main estimator for the primary estimand) include all values for change from baseline in CDAI score collected up to and including Week 12 for all participants in the primary efficacy analysis set (ie, those who were randomly assigned to study intervention and received at least one dose of study intervention). Any CDAI score collected after experiencing intercurrent event categories 1-3 will be replaced by the baseline observation for CDAI. For subjects experiencing ICE category 4, CDAI data at all visits after an ICE will be set to missing with assumption of missing at random. For ICE category 5, treatment policy strategy, the observed values after ICEs will be used, if available.

The main estimator for the primary estimand is based on the Mixed Effects Model for Repeated Measures (MMRM), under the Missing at Random (MAR) assumption for the missing responses, the missing data will be accounted for through correlation of repeated measures in the model, to test the difference between the experimental group and the placebo group. The analysis will use change in CDAI scores at post-baseline time points through Week 12 as dependent variables. The explanatory variables of the MMRM model will include the fixed, categorical effects of treatment, time, and treatment-by-time interaction, as well as the continuous, fixed covariates of baseline and baseline-by-time interaction. If the intervention cohort includes both Bio-IR and Bio-NF participants, then the biologic therapy status will be included in the MMRM model as well. An unstructured variance-covariance structure will be used to model the within-participant errors. The treatment comparison at Week 12 in terms of the least square mean difference and confidence intervals for decision making will be estimated based on this model.

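### SAP 5.3.1 sets every missing Week 12 CDAI to no change, but the primary estimand and its MMRM do this only for ICE 1-3 and treat other missing scores as MAR

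*SAP*

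**What the plan says.** SAP 5.3.1 names the primary endpoint (change from baseline in CDAI at Week 12, full analysis set) and adds: "This will apply for both interim analysis and final analysis". The main text of that section closes with: "Subjects who do not return for evaluation or have a missing CDAI score at Week 12 will be considered to have no change" from baseline. No cause of missingness is specified.

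The primary estimand (SAP 5.3.2.1) is narrower: "Participants who have intercurrent events in categories 1-3 (defined below) prior to the Week 12 visit will have their baseline CDAI score assigned". Categories 1-3 are Crohn's surgery, a prohibited medication change, and stopping treatment for lack of efficacy or worsening disease. Category 4 is stopping treatment for COVID-19 reasons, illustrated by: "like missing the assessment visit due to COVID-19 quarantine, but excluding COVID-19 infection". Category 5 is stopping for other reasons.

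The main estimator (SAP 5.3.3.1) follows the estimand: "The primary endpoint will be analyzed based on the primary estimand". For category 4, "CDAI data at all visits after an ICE will be set to missing with assumption of missing at random". For category 5, the estimand says: "For ICE category 5, treatment policy strategy, the observed values after ICEs will be used, if available". The MMRM is fitted "under the Missing at Random (MAR) assumption for the missing responses, the missing data will be accounted for through correlation of repeated measures".

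Protocol 9.4.2 refers the primary endpoint to Master protocol 9.4.2, which was not available.

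**The concern.** A Week 12 score that is missing outside ICE 1-3 has two prescribed values: zero change under 5.3.1, or missing and handled by the model under 5.3.3.1. If a programmer fills in zeros when deriving the endpoint, no missing Week 12 value is left for the MMRM or for the tipping-point analysis (Estimand 4). The estimate, interval and p-value then no longer belong to the stated primary estimand.

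SAP 5.3.3.1 also takes the confidence intervals for decision making from this model, so the choice carries into the futility and success bounds in Attachment 1. Zero change is not reliably conservative. It shrinks a true difference when missingness is balanced. When missingness is unbalanced it can move the result either way, because placebo participants are also expected to improve.

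**Working it through.** **Do the rules conflict?**

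| Week 12 score missing because of | 5.3.1 | 5.3.2.1 and 5.3.3.1 |
|---|---|---|
| ICE 1-3 | no change | baseline value (agree) |
| ICE 4 | no change | missing, MAR |
| ICE 5, no later data | no change | MAR through the MMRM |
| no ICE | no change | MAR through the MMRM |

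The only explicit precedence sentence, under Treatment Failure Rules in 5.3.1, covers treatment failure, where the two rules already agree. SAP Appendix 2 (changes to planned analyses) addresses COVID-19 events only. Sensitivity Estimator 2, the ANCOVA, uses Week 12 alone and states no missing-data rule.

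An ICE 4 participant with an observed Week 12 score is a separate case. The estimand discards that score, and 5.3.1 does not plainly catch it.

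**Inputs.** 54 active and 36 placebo; 2-sided alpha 0.1; true difference 60; SD 93 (SAP 1.2, 3 and 5.3). CDAI means and covariances come from SAP Attachment 2, with 50% Bio-IR and 50% Bio-NF.

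**Planned power.** SE = 93 × √(1/36 + 1/54) = 20.0. Power = Φ(60/20.0 − 1.645) = 91.2%, or 90.8% with the noncentral t. The plan's figure of about 90% reproduces.

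**Closed form.** Mean Week 12 improvement:

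- Active: (85 + 126)/2 = 105.5
- Placebo: (25 + 66)/2 = 45.5

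With missing fractions a (active) and p (placebo) outside ICE 1-3, unrelated to outcome, zero change estimates (1 − a) × 105.5 − (1 − p) × 45.5. MAR keeps 60.

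- Balanced at m: 60 × (1 − m)
- 20%/10%: 0.8 × 105.5 − 0.9 × 45.5 = 43.5
- 10%/20%: 0.9 × 105.5 − 0.8 × 45.5 = 58.6
- No true effect, 15%/25%: (0.85 − 0.75) × 45.5 = 4.6 points of spurious benefit

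At the planned effect, zero change is unbiased only if p/a = 105.5/45.5 = 2.3. With no effect, it is unbiased when missingness is equal.

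**Simulation.** 20,000 trials per scenario were drawn from the Attachment 2 inputs. The MMRM was fitted by REML with unstructured covariance, treatment-by-time, baseline-by-time and population. Missingness was random within arm, with the last observed visit uniform over Weeks 2, 4 and 8. With no missing data the estimate was 60.0, power 90.3%, and null error favouring active 5.1%.

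| Missing, active/placebo (assumed) | Zero-change estimate: formula | Simulated | Power, MAR | Power, zero change |
|---|---|---|---|---|
| 2%/2% | 58.8 | 58.9 | 90% | 89% |
| 5%/5% | 57.0 | 57.0 | 89% | 88% |
| 10%/10% | 54.0 | 53.8 | 87% | 84% |
| 20%/20% | 48.0 | 47.7 | 84% | 78% |
| 20%/10% | 43.5 | 43.1 | 86% | 69% |
| 10%/20% | 58.6 | 58.5 | 86% | 90% |

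With no true effect, 15%/25% missing gave a simulated bias of +4.5, and the chance of a significant result favouring active rose from 5.1% (MAR) to 7.9% (zero change). At 25%/15% the bias was −4.7 and that chance fell from 5.0% to 3.1%.

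**Cross-check.** A normal approximation with SD 93 gives the same direction: 88.5% (MAR) against 86.7% (zero change) at 10%/10%, and 87.1% against 71.8% at 20%/10%. By the same approximation, the chance of meeting the final CDAI success rule (80% lower bound at least 40) at 10%/10% is 54% under MAR and 45% under zero change.

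**The case against.** The strongest reply is that the SAP, read as a whole, shows which rule governs. Section 5.3.3.1 is the more specific text, ties the primary analysis to the estimand and states MAR. Estimand 2 exists to extend baseline values to ICE 4-5, and the tipping-point analysis would have little to act on if every missing score were already zero. This stands as evidence of intent. It does not remove a contrary rule from the endpoint definition, and it leaves the ANCOVA unspecified.

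Second, the interim-and-final sentence follows the naming of the endpoint, not the missing-data sentence. That is fair on wording, but both sit in the one section defining the endpoint for both analyses. No interim effect was calculated here.

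Third, the quarantine example illustrates treatment discontinuation, so a missed visit alone is not clearly ICE 4. That example is therefore less clean than it looks. The conflict does not depend on it, since scores missing after ICE 5 or without an ICE are caught in the same way.

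Fourth, the missing rates are assumed and may be low. Participants who stop treatment are still asked to attend visits (Protocol 1.3, footnote c), and 4 of 8 components suffice for a CDAI score. The simulation also makes MAR true by construction, so informative dropout is untested. Both limits stand. The decision framework is non-binding too, but the primary test still uses these data.

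**Conclusion.** The concern holds and should be fixed. The SAP contains two incompatible rules for a Week 12 CDAI missing outside ICE 1-3, and the one in the endpoint definition, applied as written, gives a result that is not the primary estimand's. Confidence is high on the conflict itself.

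The size depends on missing rates the documents do not give. At 5% or below in each arm it is about 1 point of power. At 10% to 20%, or with unequal arms, it is material and can go in either direction. The planned sample size and the stated power are unaffected. Master protocol 9.4.2 was not seen and may settle the point.

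**What to change.** In SAP 5.3.1:

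- Limit the no-change rule to ICE 1-3. Deleting the sentence would also serve, since the treatment failure rules already cover those events.
- State that any other missing Week 12 CDAI stays missing and is handled by the MMRM under MAR, at both interim and final.

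In SAP 5.3.3.2, state how the ANCOVA (Sensitivity Estimator 2) treats a missing Week 12 score. Confirm that Master protocol 9.4.2 agrees.

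If the sponsor wants to keep the all-missing-as-no-change rule, it can stay as a labelled sensitivity analysis. It would differ from Estimand 2 by also zeroing scores missing without an ICE, and by leaving observed scores after ICE 4-5 in place.

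The cost is two or three SAP sentences before unblinding, with no change to conduct or sample size.

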### **Treatment Failure Rules:**

Treatment failure rules will be applied for all efficacy endpoints unless otherwise specified. In such a case, baseline values (at Week 0) will be assigned from the point of treatment failure onward, regardless of the observed data, for continuous endpoints, and participants will be considered as not achieving the respective endpoints for dichotomous endpoints. Treatment failure rules override other data handling rules.

For dichotomous endpoints, participants who have a treatment failure are considered as not achieving the respective endpoints after treatment failure. For continuous endpoints, participants who have a treatment failure will have their baseline values carried forward after treatment failure onwards.

The treatment failure rules will be applied to determine the final CDAI score. The treatment failure rules override the actual observation of the CDAI score. Participants who have any of the following events prior to the Week 12 visit will be considered a treatment failure and will be considered to have no change at Week 12 from their baseline CDAI score, regardless of the actual CDAI score:

- A Crohn's disease-related surgery (with the exception of drainage of an abscess or seton placement)
- Discontinuation of study intervention due to lack of efficacy or due to an adverse event (AE) of worsening Crohn's disease
- Specified changes in concomitant Crohn's disease medications described below.

The treatment failure rules for physician prescribed concomitant medication changes between Week 0 and Week 12 are:

1. Corticosteroids:
  - a. Initiation of oral corticosteroids (excluding budesonide) due to worsening Crohn's disease.
  - b. Initiation of oral corticosteroids (excluding budesonide) for more than 7 days due to reasons other than worsening Crohn's disease.
  - c. Initiation of oral budesonide due to worsening Crohn's disease.
  - d. Initiation of oral budesonide for more than 7 days due to reasons other than worsening Crohn's disease.
  - e. Increase by  $\geq 5$  mg above baseline in the prednisone equivalent dosage of oral corticosteroids (excluding budesonide) due to worsening Crohn's disease.
  - f. Increase by  $\geq 5$  mg above baseline in the oral prednisone equivalent dosage of oral corticosteroids (excluding budesonide) for more than 7 days due to reasons other than worsening Crohn's disease.
  - g. Increase by  $\geq 3$  mg above baseline in the dose of oral budesonide due to worsening Crohn's disease.
  - h. Initiation of IV corticosteroids due to worsening Crohn's disease.
  - i. Initiation of rectal corticosteroids due to worsening Crohn's disease.
2. 5-ASA compounds:
  - a. Initiation or increase of oral 5-ASA compounds due to worsening Crohn's disease.
3. Immunomodulator agents:
  - a. Initiation of oral 6-MP/AZA due to worsening Crohn's disease.
  - b. Initiation of oral, subcutaneous, or intramuscular MTX due to worsening Crohn's disease.
  - c. Increase above baseline in the dose of oral 6-MP/AZA due to worsening Crohn's disease.
  - d. Increase above baseline in the dose of oral, subcutaneous, or intramuscular MTX due to worsening Crohn's disease (with the same route).
4. Protocol-prohibited medications:

An initiation of any of the following after baseline due to worsening Crohn's disease:

  - a. Immunomodulatory agents other than 6-MP/AZA or MTX (including but not limited to 6-TG, cyclosporine, tacrolimus, sirolimus, mycophenolate mofetil).
  - b. Immunomodulatory biologic agents (including but not limited to TNF antagonists, natalizumab, abatacept).
  - c. Experimental Crohn's disease medications (including but not limited to thalidomide, briakinumab, vedolizumab, traficet, AMG 827).
5. Crohn's disease related antibiotics:
  - a. Initiation or change of antibiotics due to worsening Crohn's disease.

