4.2.1. Study-Specific Ethical Design Considerations

The primary ethical concern is that participants enrolled in an intervention cohort will be randomized to receive either active study intervention or placebo for 12 weeks, with no therapeutic benefit for this portion of the study. While patients with Crohn's disease do traditionally benefit from inclusion in clinical studies independent of the assigned therapy and many improve even while on placebo (up to 30-50%), the duration of the placebo-controlled induction period has been limited to the extent possible while still maintaining sufficient scientific rigor for meaningful evaluation of critical endoscopic endpoints. Also, participants will be closely monitored during this 12-week period and will continue to receive existing background therapy for Crohn's disease. Participants with worsening Crohn's disease can discontinue the study intervention at any time, and the study intervention should be discontinued if a participant requires additional therapy for Crohn's disease.

The total blood volume to be collected is considered to be an acceptable amount of blood to be collected over this time period from the population in this study and is described Section 8 of this ISA.

Refer to Section 4.2.1 of the Master protocol PLATFORMPACRD2001 for other study-specific ethical design considerations.

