7. Initiation of total (complete) or partial (supplemental) parenteral nutrition administered through any indwelling catheter <3 weeks before baseline or anticipated to require parenteral nutrition administered through an indwelling catheter during enrollment in the study	
8. Initiation of enteral therapy for Crohn's disease (liquid nutritional formula comprising \geq 80% of total caloric intake administered through the gastrointestinal tract) <3 weeks before baseline. Subjects who are on a stable regimen of enteral feeds \geq 3 weeks before baseline may be considered for enrollment if they plan to continue enteral feeds as treatment for Crohn's disease through the duration of the study.	

Infections or Predisposition to Infections

9. Has a history of serious infection (eg, sepsis, pneumonia, or pyelonephritis), including any infection requiring hospitalization or IV antibiotics, within 8 weeks before baseline

10. Has a stool culture or other examination positive for an enteric pathogen, including *Clostridium difficile* toxin, in the last 4 months unless a repeat examination is negative and there are no signs of ongoing infection with that pathogen, or has had a fecal transplant in the last 4 months

11. Has a history of, or ongoing, chronic or recurrent infectious disease, including but not limited to, chronic renal infection, chronic chest infection, recurrent urinary tract infection (eg, recurrent pyelonephritis or chronic nonremitting cystitis), or open, draining, or infected skin wounds or ulcers
12. Has current signs or symptoms of infection. Established nonserious infections (eg, acute upper respiratory tract infection, simple urinary tract infection) need not be considered exclusionary at the discretion of the investigator
13. Has or ever has had a systemic nontuberculous mycobacterial infection or serious opportunistic infection (eg, cytomegalovirus colitis, *Pneumocystis carinii*, aspergillosis)
14. Is infected with human immunodeficiency virus (HIV; positive serology for HIV antibody). If seropositive, consultation with a physician with expertise in the treatment of HIV is recommended
15. Is seropositive for antibodies to hepatitis C virus (HCV) without a history of successful treatment, defined as being negative for HCV RNA at least 24 weeks after completing antiviral treatment

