6.5.2. Crohn's Disease-Specific Therapies

Participants must continue to receive their concomitant, background oral 5-ASA compounds, the immunomodulators AZA, 6-MP, and MTX, oral corticosteroids, and/or antibiotics for the treatment of Crohn's disease during the study (as defined in the inclusion criteria). **Concomitant medications for Crohn's disease at study enrollment should be maintained at a stable dose throughout this study.**

Enrolled participants **should not initiate** any of the following Crohn's disease-specific medical therapies during their participation in the study:

- Oral or rectal 5-ASA compounds
- Immunomodulators (ie, AZA, 6-MP, or MTX)
- Parenteral or rectal corticosteroids
- Antibiotics as a treatment for Crohn's disease
- Total parenteral nutrition as a treatment for Crohn's disease

Because protection of human research participants is paramount, it is recognized that initiating or modifying the dose of the above therapies may be medically required. If the above medications are initiated or medication doses are changed, participants may continue to receive the study

intervention, and should continue to attend all study visits and have all assessments. If due to medical necessity in the opinion of the investigator, the above medications are initiated or medication doses are changed, this does not represent a deviation from the study protocol, but may be considered a treatment failure.

Oral corticosteroid should not be initiated during the study.

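### Nutritional therapy started for worsening Crohn's disease is missing from the SAP failure list and from ICE 2; the gap is narrow and its effect small

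*SAP*

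**What the plan says.** **SAP.** Section 5.3.1 counts three things as treatment failure: Crohn's surgery, stopping drug for lack of efficacy or an adverse event of worsening Crohn's disease, and "Specified changes in concomitant Crohn's disease medications described below". The medication list has five classes: corticosteroids, 5-ASA (oral route only), immunomodulators, protocol-prohibited medications, and antibiotics. Its last item is "Initiation or change of antibiotics due to worsening Crohn's disease". There is no nutrition entry and no catch-all. From the point of failure the baseline CDAI is assigned.

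In 5.3.2.1, ICE 2 is "A prohibited change in CD medication". ICE 3 is a drug stop for lack of efficacy or worsening disease. Both are handled by the composite strategy, so baseline is assigned. ICE 5 is a drug stop for other reasons and is handled by treatment policy, so observed values are kept.

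**Protocol (ISA).**
- Exclusion criterion 8 bars enteral therapy begun within 3 weeks before baseline. It allows people on a stable regimen "if they plan to continue enteral feeds as treatment for Crohn's disease through the duration of the study".
- Section 6.5.2 puts "Total parenteral nutrition as a treatment for Crohn's disease" on its list of therapies not to be started. It lets participants who start a listed therapy stay on drug, and says of a medically necessary start that "this does not represent a deviation from the study protocol, but may be considered a treatment failure".
- Section 7.1 requires drug to stop when total or partial parenteral nutrition is begun through an indwelling catheter.
- Enteral therapy is not named in 6.5.1, 6.5.2, 6.5.3 or 7.1.
- More generally, 4.2.1 says "the study intervention should be discontinued if a participant requires additional therapy for Crohn's disease". Section 7.1 asks that stopping be considered when disease worsens and continuing is not in the participant's interest. Sections 2.3.1 and 2.3.3 speak of withdrawal, or of stopping drug, in similar circumstances.

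**The concern.** The protocol treats nutrition as Crohn's therapy: it controls enteral therapy at entry and lists parenteral nutrition beside 5-ASA, immunomodulators, corticosteroids and antibiotics. The SAP turns each of those drug classes into a failure rule but not nutrition. Two participants rescued for the same reason can therefore be scored differently. One who starts oral 5-ASA or an antibiotic for worsening disease gets the baseline CDAI. One who starts enteral formula and stays on drug keeps whatever CDAI is recorded on the formula.

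The supplementary estimands do not test the enteral case. Estimands 2 and 3 act only after an ICE, and the tipping-point analysis adjusts participants who discontinued. For parenteral nutrition, the score can turn on how the reason for stopping drug is coded, or on which of 6.5.2 and 7.1 the site follows.

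**Working it through.** **Step 1. Route of each therapy, when started for worsening disease and no other failure rule is met.**

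| Therapy and course | Category | CDAI used |
|---|---|---|
| Parenteral; drug stopped under 7.1, coded lack of efficacy or worsening disease | ICE 3 | baseline |
| Parenteral; drug stopped, coded to another reason | ICE 5 | observed (Estimand 2 tests this) |
| Parenteral; drug continued under 6.5.2 | none, unless ICE 2 is read to include it | observed, or baseline on that reading |
| Enteral; drug stopped in line with 4.2.1 or 7.1, coded as worsening disease | ICE 3 | baseline |
| Enteral; drug continued | none | observed |

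The wider reading of ICE 2 is possible for total parenteral nutrition because 6.5.2 refers to its whole list as medications. It does not extend to enteral therapy, which no supplied section bars after baseline.

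**Step 2. The plan's own power figure.** SAP section 3 gives a difference of 60, SD 93 and about 90% power; the arms are 54 and 36 and alpha is 0.1 two-sided.
- SE = 93 x sqrt(1/54 + 1/36) = 20.01.
- Power = Phi(60/20.01 - 1.645) = 91.2%. The stated figure reproduces.

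**Step 3. SE from the simulation assumptions** (protocol Appendix 6, Week 12 given Week 0).
- Bio-IR: 11025 - 3255^2/3844 = 8268.75.
- Bio-NF: 11025 - 2520^2/3600 = 9261.0.
- Mean 8764.9, so SD = 93.62 and SE = 93.62 x sqrt(1/54 + 1/36) = 20.14.
- Power at 60 = Phi(60/20.14 - 1.645) = 90.9%.

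**Step 4. Effect of one case.** Let g be the on-rescue improvement from baseline at Week 12 (negative means worse). The difference is placebo minus active, so a larger value favours the drug. Keeping the observed score instead of baseline shifts it by -g/36 for a placebo case and +g/54 for an active case. The documents give no value for g. I assume -50 to 150, and also show the Appendix 6 placebo mean falls: 323 - 298 = 25 (Bio-IR) and 302 - 236 = 66 (Bio-NF).

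| One case | g | Shift | Shift/SE | Power |
|---|---|---|---|---|
| Placebo | -50 | +1.39 | +0.07 | 92.0% |
| Placebo | 0 | 0 | 0 | 90.9% |
| Placebo | 25 | -0.69 | -0.03 | 90.3% |
| Placebo | 66 | -1.83 | -0.09 | 89.3% |
| Placebo | 150 | -4.17 | -0.21 | 87.0% |
| Active | -50 | -0.93 | -0.05 | 90.1% |
| Active | 150 | +2.78 | +0.14 | 92.9% |

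Shifts add. Four placebo cases and no active case, each 100 points better than baseline, would give -4 x 100/36 = -11.1 points and power of 78.8% (SD 93). Equal proportions with equal changes in the two arms cancel. These are simple mean shifts with the SD held fixed; they approximate the MMRM.

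**The case against.** The strongest reply is that nothing is broken. The SAP does not promise to score every rescue as failure; it scores specified changes, and does so selectively. Steroid increases for worsening disease count only from 5 mg prednisone-equivalent or 3 mg budesonide, and only oral 5-ASA is listed. The protocol itself leaves the 6.5.2 therapies as possible failures. Which co-interventions enter a composite is a design choice. That stands, and it is why this is an improvement and not an inconsistency with a stated rule.

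A second reply is that several texts push a worsening participant off drug: 4.2.1, the 7.1 advice, and sections 2.3.1 and 2.3.3. A stop made for those reasons would ordinarily be ICE 3. That also stands, and it narrows the enteral case. It does not close it, because these are general statements, enteral therapy is not among the mandatory stops in 7.1, and 6.5.2 lets participants stay on drug after comparable rescue.

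A reader might infer that nutritional rescue as a whole escapes the failure rules. The documents do not support this: parenteral nutrition normally reaches ICE 3. A reader might also infer a known bias against the drug. That needs more rescue on placebo and scores better than baseline, and neither is given; a rescued participant may still end worse than baseline.

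Finally, the ISA defers discontinuation, efficacy assessment, general analysis considerations and the primary endpoint analysis to the Master protocol, which was not available. A rule may sit there. The SAP list nevertheless reads as closed.

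**Conclusion.** The gap is real but narrow. The failure list omits one class named in 6.5.2, parenteral nutrition, and no supplied on-study rule names enteral therapy. An on-rescue CDAI is kept only along the residual routes in Step 1, and only when no surgery, steroid, 5-ASA, immunomodulator, antibiotic or prohibited-drug rule applies. Such cases are probably rare, since short gut, symptomatic strictures and anticipated parenteral nutrition are excluded at entry.

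At the final analysis, one case moves the treatment difference by about 0.2 SE at most over the assumed range, in either direction, with power between 87.0% and 92.9% against 90.9%. The rate and the on-rescue change are both assumptions. A material effect would need several cases concentrated in one arm, and nothing in the documents points to that. Minor, with medium confidence because the Master protocol is unseen.

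**What to change.** 1. In SAP 5.3.1 and in ICE 2 of the primary estimand, add: starting, after Week 0 and because of worsening Crohn's disease, either total or partial parenteral nutrition or enteral formula prescribed as treatment for Crohn's disease (not supplements added to a normal diet). Assign baseline from that point, whatever reason is coded for any drug stop.
2. In protocol 6.5.2, add enteral therapy to the therapies not to be started, and make the section agree with 7.1 that drug stops when parenteral nutrition begins.
3. Leave the Table 2 footnote on endoscopic response unchanged. It lists only prohibited agents, not conventional steroids, 5-ASA or antibiotics, so adding nutrition would make formula feeding a failure there when starting a steroid is not.

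Apply the rule from the treatment description and indication that protocol 6.5 already has recorded. The 80%-of-calories definition in exclusion criterion 8 would need a field that is not listed as collected. The cost is one more category to adjudicate while blinded, and possibly a participant or two more scored as no change.
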